9.3.2 Analysis of Key Secondary Variables

9.3.2.1 Definition of Variables

Sweat chloride (SwCl): the SwCl value for a given visit will be calculated as the mean of the non-missing sweat chloride measurements obtained on the left and right arms at that visit. If one of the two arm measurements at a time point is missing, the other will be used as the mean. A volume ≥ 15 μL is required for an accurate determination of sweat chloride. Any results reported as having volume < 15 μL will be considered missing. Any sweat chloride values reported as > 160 mmol/L will be considered missing. Any sweat chloride values reported as < 10 mmol/L will be imputed as 10 mmol/L.

9.3.2.2 Analysis Method

Absolute change in SwCl from baseline through Week 8 for the ELX/TEZ/IVA group:

Analysis of this endpoint will be based on the same MMRM model as the analysis of the primary efficacy endpoint. Data obtained from the Day 15, Week 4, and Week 8 Visits will be included in the model. Absolute change in SwCl from baseline through Week 8 is defined as average of Day 15, Week 4, and Week 8.

Absolute change in ppFEV₁ from baseline through Week 8 for the ELX/TEZ/IVA group compared to the control group:

Analysis of this endpoint will be based on the same MMRM model as the analysis of the primary efficacy endpoint. Data obtained from the Day 15, Week 4, and Week 8 Visits will be included in the model. However, the Day 15 Visit will not be included in the estimation of the average treatment effect through Week 8.

Absolute change in SwCl from baseline through Week 8 for the ELX/TEZ/IVA group compared to the control group:

Analysis of this endpoint will be based on the same MMRM model as the analysis of the primary efficacy endpoint. Data obtained from the Day 15, Week 4, and Week 8 Visits will be included in the model. Absolute change in SwCl from baseline through Week 8 is defined as average of Day 15, Week 4, and Week 8.

The LS mean (SE) of the within-treatment group change from baseline at each post-baseline visit up to Week 8 along with the 95% CI will be estimated from the corresponding MMRM. The LS mean (SE) of the treatment difference between ELX/TEZ/IVA and control at each post-baseline visit will be provided along with the corresponding 95% CI and *P* value. The LS mean (SE) at each visit will also be plotted by treatment group. In addition, the post-baseline raw values and the absolute change from baseline at each post-baseline visit up to Week 8 will be summarized descriptively (n, mean, SD, median, minimum, and maximum).

9.3.2.3 Multiplicity Adjustment

A hierarchical testing procedure will be used to control the overall type I error at an alpha of 0.05 for the primary endpoint and the key secondary endpoints tested. The key secondary endpoints will only be tested at an alpha of 0.05 if the primary endpoint of absolute change in ppFEV₁ from baseline through Week 8 for the ELX/TEZ/IVA group is statistically significant. For a test at any step to be considered statistically significant within the testing hierarchy, it must be statistically

significant, and all previous tests (if any) within the hierarchy must be statistically significant at the 0.05 level. The testing order of the key secondary endpoints is as follows:

- First key secondary endpoint: Absolute change in SwCl from baseline through Week 8 for the ELX/TEZ/IVA group
- Second key secondary endpoint: Absolute change in ppFEV₁ from baseline through Week 8 for the ELX/TEZ/IVA group compared to the control group
- Third key secondary endpoint: Absolute change in SwCl from baseline through Week 8 for the ELX/TEZ/IVA group compared to the control group

9.3.2.4 Sensitivity Analysis

To assess the impact of including extreme small sweat chloride values, a sensitivity analysis will be conducted in which case any sweat chloride values reported as <10 mmol/L will be considered as missing. This sensitivity analysis only applies to the absolute change from baseline in SwCl. An MMRM analogous to the analysis of SwCl described in Section 9.3.2.2 will be conducted and the relevant estimators will be reported.

9.3.3 Analysis of Other Secondary Efficacy Variables

9.3.3.1 Definition of Variables

Cystic Fibrosis Questionnaire-Revised (CFQ-R): The CFQ-R^{3,4,5} is a validated CF-specific instrument that measures quality-of-life domains. This study utilizes three different versions of CFQ-R:

- CFQ-R for Children ages 12 and 13
- CFQ-R for Adolescents and Adults (subjects 14 years and older)
- CFQ-R for Parents/Caregivers (subjects 13 years and younger)

In all three versions, specific question belonging to a domain is scored 1, 2, 3, or 4. The CFQ-R domain score, e.g., physical domain score or respiratory domain score, is defined as a scaled score as follows:

$$\text{Scaled score for a domain} = 100 \times (\text{mean (scores of all questions in the domain)} - 1)/3,$$
where the score from a negatively phrased question is first reversed, i.e., reversed score = 5 – actual score, so that 1 always represents the worst condition and 4 the best condition. The (scaled) domain score ranges from 0 (worst condition) to 100 (best condition). The scaled score for a specific domain will not be calculated if more than half of the questions in the domain have missing scores.

The (scaled) domain score from the CFQ-R for Children ages 12 and 13 and for Adolescent and Adults will be pooled for the analysis purpose.

9.3.3.2 Analysis Method

Other secondary efficacy endpoints include:

Absolute change in CFQ-R RD score from baseline through Week 8 for the ELX/TEZ/IVA group:

Absolute change in CFQ-R RD score from baseline through Week 8 for the ELX/TEZ/IVA group compared to the control group:

Analysis of both endpoints will be based on an MMRM model similar to the analysis of the primary efficacy endpoint. Data obtained from the Day 15, Week 4, and Week 8 Visits will be included in the model. However, the Day 15 Visit will not be included in the estimation of the average treatment effect through Week 8. The analysis will include pooled CFQ-R RD score assessed at clinic and at home. An additional analysis may be performed to include only the clinic assessed CFQ-R RD score, if the home assessed data are inconsistent with the clinic assessed data.

In addition, similar analyses may be performed, if the CFQ-R RD score collected prior to the outbreak of COVID-19 (defined as March 2, 2020) are inconsistent with the data collected during COVID-19, for the cohort of subjects who complete week 8 before the outbreak of COVID-19. Such analysis results should be interpreted with caution due to small sample size.

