12.3.3.3 Analysis of Other Secondary Efficacy Endpoints

Other secondary efficacy endpoints include:

- **Absolute change in CFQ-R RD score from baseline through Week 8 for the VX-445/TEZ/IVA group:** Analysis of this endpoint will be based on an MMRM model similar to the analysis of the primary efficacy endpoint. Data obtained from the Day 15, Week 4, and Week 8 Visits will be included in the model. However, the Day 15 Visit will not be included in the estimation of the average treatment effect through Week 8.
- **Absolute change in CFQ-R RD score from baseline through Week 8 for the VX-445/TEZ/IVA group compared to the control group:** Analysis of this endpoint will be based on an MMRM model similar to the analysis of the primary efficacy endpoint. Data obtained from the Day 15, Week 4, and Week 8 Visits will be included in the model. However, the Day 15 Visit will not be included in the estimation of the average treatment effect through Week 8.

Details will be provided in the SAP.

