12.3.3.5 Analysis of Exploratory Efficacy Endpoints

Exploratory efficacy endpoints include:

- **Absolute change in CFQ-R non-RD scores from baseline through Week 8:** Analysis of this endpoint will be based on an MMRM model similar to the analysis of the primary efficacy endpoint. Data obtained from the Day 15, Week 4, and Week 8 Visits will be included in the model. However, the Day 15 Visit will not be included in the estimation of the average treatment effect through Week 8.
- **Absolute change in BMI from baseline at Week 8:** Analysis of this endpoint will be based on an MMRM model similar to the analysis of the primary efficacy endpoint. Data obtained from the Day 15, Week 4, and Week 8 Visits will be included in the model.

Additional details will be specified in the SAP.

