9.3.1.2 Primary Analysis

The primary analysis will be performed using a mixed-effects model for repeated measures (MMRM) with the absolute change from baseline at Day 15, Week 4 and Week 8 as the dependent variable. The model will include treatment group, visit, and treatment-by-visit interaction as fixed effects, with continuous baseline ppFEV₁, continuous baseline SwCl, and comparator group (IVA comparator versus TEZ/IVA comparator) as covariates. The Day 15 Visit will not be included in the estimation of the average treatment effect through Week 8. The model will be estimated using restricted maximum likelihood. Denominator degrees of freedom for the *F*-test for fixed effects will be estimated using the Kenward-Roger approximation². An unstructured covariance structure will be used to model the within-subject errors. If the model estimation does not converge, a compound symmetry covariance structure will be used instead. Conditional on the observed data and covariates, missing data will be assumed to be missing at random; consequently, no imputation of missing data will be performed.

The primary results obtained from the model will be the estimated within-group treatment difference through Week 8 (average of Week 4 and Week 8) for the ELX/TEZ/IVA group. The adjusted means with 2-sided 95% confidence intervals and 2-sided *P* values will be provided. Furthermore, the within-group treatment difference at each post-baseline visit will also be provided, obtained from the model.

The adjusted mean (with SE) obtained from the MMRM analysis at each post-baseline visit up to Week 8 will be plotted by treatment group.

The primary analysis will be conducted with the clinic spirometry data only. An additional analysis may also be performed to include pooled spirometry data obtained in clinic and by Air Next Spirometer, if the Air Next Spirometry data are assessed to be reasonably consistent with clinic spirometry data.

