9.3.1.5 Subgroup Analysis

Subgroup analyses of the primary efficacy endpoint will be performed using a model similar to that of the primary analysis for each of the following subgroups. The primary result obtained from the model will be estimated within-treatment difference through Week 8 (average of Week 4 and Week 8) for the ELX/TEZ/IVA group:

- Age at Screening (<18, ≥18 years)
- ppFEV₁ at baseline (< 70, ≥ 70)
- Comparator group (TEZ/IVA comparator, IVA comparator)
- Sex (male, female)
- Geographic region (North America, Europe)

The MMRM used for the primary analysis will be used for the subgroup analysis, where the same model will be applied to each category of the subgroup. Note that for the subgroup analysis based on comparator group, the covariate of comparator group (TEZ/IVA comparator, IVA comparator) from the MMRM will be removed. The adjusted means with 2-sided 95% confidence intervals will be provided. Furthermore, estimated within-treatment difference through Week 8 (average of Week 4 and Week 8) for the ELX/TEZ/IVA group in different categories within a subgroup will also be presented in a forest plot. Note: The purpose of subgroup analysis is to assess trend consistency; not hypothesis testing with sufficient power. Due to potential small sample size, the results from above mentioned subgroup analysis, especially the comparison between two comparator groups, should be interpreted with caution.

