9.3.4.2 Analysis Method

Absolute change in CFQ-R non-respiratory domain scores from baseline through Week 8: (Pooled 'Children Ages 12 and 13' Version and 'Adolescents and Adults' Version): Analysis of this endpoint will be based on an MMRM model similar to the analysis of the primary efficacy endpoint. Data obtained from the Day 15, Week 4, and Week 8 Visits will be included in the model. However, the Day 15 Visit will not be included in the estimation of the average treatment effect through Week 8.

Absolute change in BMI from baseline at Week 8:

Analysis of these endpoints will be based on an MMRM model similar to the analysis of the primary efficacy endpoint. Data obtained from the Day 15, Week 4, and Week 8 Visits will be included in the model. No *P*-values will be provided for exploratory variables.

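### Does calling the CFQ-R models only similar to the primary MMRM, without naming the CFQ-R baseline as a covariate, call for a change?

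*SAP*

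**What the plan says.** The primary MMRM (SAP 9.3.1.2; likewise Protocol 12.3.3.1) is fitted "with continuous baseline ppFEV₁, continuous baseline SwCl, and comparator group (IVA comparator versus TEZ/IVA comparator) as covariates". No other covariate list is given for any efficacy MMRM.

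The remaining efficacy models refer back to it in two ways:

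- **Key secondary endpoints** (sweat chloride, and ppFEV₁ against control; SAP 9.3.2.2): "Analysis of this endpoint will be based on the same MMRM model as the analysis of the primary efficacy endpoint".
- **CFQ-R RD** (SAP 9.3.3.2): "Analysis of both endpoints will be based on an MMRM model similar to the analysis of the primary efficacy endpoint".
- **CFQ-R non-RD domains** (SAP 9.3.4.2): "Analysis of this endpoint will be based on an MMRM model similar to the analysis of the primary efficacy endpoint". BMI, in the same section, has equivalent wording.

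The protocol draws the same distinction and leaves the rest to the SAP: "Details will be provided in the SAP" (12.3.3.3) and "Additional details will be specified in the SAP" (12.3.3.5). For CFQ-R RD the SAP then gives the visits, the exclusion of Day 15 from the average, and the rules for home and pre-pandemic data, but no covariates.

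Baseline CFQ-R is available. The questionnaire is completed on Day 1 (Protocol Table 3-2), and the baseline RD score is summarised as a disease characteristic (SAP 9.2.2).

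**The concern.** A change-from-baseline model normally adjusts for the baseline of the variable analysed. Read literally, the CFQ-R models would adjust for baseline lung function and sweat chloride but not for baseline CFQ-R. Randomisation is not stratified on CFQ-R either (SAP 7.3), so nothing named in the model would deal directly with a chance imbalance in the starting score.

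What would be at stake is precision. CFQ-R RD is the only patient-reported secondary endpoint, and its comparison with control would have a wider interval than data already in hand allow. Two programmers could also read *similar* differently and fit different models.

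**Working it through.** **1. The plan's own figures.** The documents give no SD, correlation, target difference or power for CFQ-R. The only power statement concerns the within-group ppFEV₁ test: SD 7.0, difference 3.0, 125 subjects less 10% dropout. It reproduces (99.4% at n = 112, against the stated figure of more than 99%) but says nothing about CFQ-R.

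**2. The wording, side by side.**

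| Outcome | Word used | Own baseline in the primary list? |
|---|---|---|
| ppFEV₁ against control | same | yes |
| Sweat chloride | same | yes |
| CFQ-R RD | similar | no |
| CFQ-R non-RD domains | similar | no |
| BMI | similar | no |

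The wording changes exactly where the outcome's own baseline drops out of the list. That fits a model of the same form with the baseline term adapted to the outcome. The text does not say so outright.

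**3. The cost if the list were carried over unchanged.** Assume unit variance at every visit. Let B be the baseline score, M the mean of the Week 4 and Week 8 scores, and b the slope of M on B. The outcome is M − B.

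- Variance without B in the model: Var(M) + 1 − 2 Cov(M, B).
- Variance with B in the model: Var(M) − Cov(M, B)².
- The difference is (1 − b)² Var(B), which is zero when b = 1.

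Under compound symmetry with between-visit correlation ρ, and with ppFEV₁ and sweat chloride unrelated to CFQ-R, the two variances are 1.5(1 − ρ) and (1 − ρ)(1 + 2ρ)/2. The ratio of interval widths is therefore √[3/(1 + 2ρ)]:

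| ρ (assumed) | 0.4 | 0.5 | 0.6 | 0.7 | 0.8 |
|---|---|---|---|---|---|
| Width ratio | 1.29 | 1.22 | 1.17 | 1.12 | 1.07 |

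Without compound symmetry, for assumed correlations baseline–Week 4 / baseline–Week 8 / Week 4–Week 8:

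- 0.5/0.4/0.7: Var(M) = (1 + 0.7)/2 = 0.85 and Cov(M, B) = 0.45. The variances are 0.85 + 1 − 0.90 = 0.950 and 0.85 − 0.2025 = 0.648, so the width ratio is 1.21.
- 0.6/0.5/0.7: 0.750 against 0.548, ratio 1.17.
- 0.8/0.7/0.85: 0.425 against 0.363, ratio 1.08.

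If the carried-over covariates explained 20% of baseline CFQ-R, then over ρ from 0.4 to 0.8 the ratio would run from 1.24 to 1.06 when they relate to follow-up only through baseline CFQ-R, and from 1.41 to 1.10 when they correlate equally with the score at every visit. Across all these assumptions the range is 1.00 (slope 1) to 1.41.

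**4. Validity.** In simulation (4,000 trials, 112 per arm, ρ = 0.5, no treatment effect) the means of both estimators lay within 0.0011 SD of zero. Omitting the baseline widens the interval; it does not bias the randomised comparison.

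**5. Where it could matter.** The hierarchy in SAP 9.3.2.3 covers the primary and the three key secondary endpoints; CFQ-R is not in it. The non-RD domains and BMI are exploratory, are not defined as comparisons with control, and get no P values (SAP 9.3.4.2). Only the between-arm CFQ-R RD estimate is left, and that is an other secondary endpoint.

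**The case for a change.** The best evidence for a literal carry-over is SAP 9.3.1.5. Subgroup analyses are described as "using a model similar to that of the primary analysis for each of the following subgroups". The section then applies the primary MMRM and spells out its one departure, for the comparator-group subgroups: "the covariate of comparator group (TEZ/IVA comparator, IVA comparator) from the MMRM will be removed". On that pattern, silence in 9.3.3.2 and 9.3.4.2 would mean no departure. Naming the covariate would also cost only a line, 9.3.3.2 was itself revised in SAP Version 2.0, and the possible clinic-only and pre-pandemic CFQ-R analyses would inherit whatever model is chosen, the latter in a small cohort.

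Part of this stands. The text does not decide the question, the cost of a line is trivial, and the loss is real if the baseline is left out and the slope is not 1. The internal programming-rules document mentioned in SAP 9.1 may settle it, but it is described only in general terms and cannot be relied on.

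The subgroup analogy is weaker than it looks. The outcome there is still ppFEV₁, whose baseline is already in the model, so there was no baseline term to adapt. The section also shows that *similar* can cover a model whose covariates change to suit the analysis. Nor is there a single right addition: adding the CFQ-R baseline to the list and putting it in place of baseline ppFEV₁ are both defensible, and nothing in the documents separates them.

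**Conclusion.** No change to the plan follows. The covariates of the CFQ-R and BMI models are not listed, but the move from *same* to *similar* makes an adapted baseline term the likeliest reading, and adjusting for the outcome's own baseline is what an analyst would ordinarily do. If that is what is meant, nothing is lost.

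If it is not, the between-arm CFQ-R RD estimate remains unbiased and valid, with an interval about 1.07 to 1.29 times as wide for assumed correlations of 0.8 to 0.4 under compound symmetry, and no wider at a slope of 1. Those figures rest wholly on assumed correlations, and with no CFQ-R target difference or power in the documents they cannot show that any CFQ-R conclusion would change. No gain is claimed for the within-group CFQ-R endpoint. The primary result, the key secondary results and type I error control are the same on either reading.

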9.3.4 Analysis of Exploratory Variables

9.3.4.1 Definition of Variables

Body mass index (BMI): the BMI at each visit is calculated using the weight and height at each visit as follows:

$$BMI = \frac{\text{Weight (kg)}}{\text{Height}^2 \text{ (m}^2\text{)}}$$

9.3.4.2 Analysis Method

Absolute change in CFQ-R non-respiratory domain scores from baseline through Week 8: (Pooled 'Children Ages 12 and 13' Version and 'Adolescents and Adults' Version): Analysis of this endpoint will be based on an MMRM model similar to the analysis of the primary efficacy endpoint. Data obtained from the Day 15, Week 4, and Week 8 Visits will be included in the model. However, the Day 15 Visit will not be included in the estimation of the average treatment effect through Week 8.

Absolute change in BMI from baseline at Week 8:

Analysis of these endpoints will be based on an MMRM model similar to the analysis of the primary efficacy endpoint. Data obtained from the Day 15, Week 4, and Week 8 Visits will be included in the model. No *P*-values will be provided for exploratory variables.

9.3.5 Analysis of Additional Efficacy Variables

9.3.5.1 Analysis of Additional Spirometry Variables

Summary statistics for the following spirometry measurements will be presented by treatment group at each visit up to Week 8:

- FEV₁:
 - Absolute change from baseline in FEV₁ (L)
 - Relative change from baseline in FEV₁ (%)
 - Absolute change from baseline in percent predicted FEV₁ (percentage points)
 - Relative change from baseline in percent predicted FEV₁ (%)

- FVC:
 - Absolute change from baseline in FVC (L)
 - Relative change from baseline in FVC (%)
 - Absolute change from baseline in percent predicted FVC (percentage points)
 - Relative change from baseline in percent predicted FVC (%)

- FEF_{25-75%}:
 - Absolute change from baseline in FEF_{25-75%} (L/sec)
 - Relative change from baseline in FEF_{25-75%} (%)
 - Absolute change from baseline in percent predicted FEF_{25-75%} (percentage points)
 - Relative change from baseline in percent predicted FEF_{25-75%} (%)

- FEV₁/FVC:
 - Absolute change from baseline in FEV₁/FVC
 - Relative change from baseline in FEV₁/FVC (%)
 - Absolute change from baseline in percent predicted FEV₁/FVC (percentage points)
 - Relative change from baseline in percent predicted FEV₁/FVC (%)

9.4 Safety Analysis

All safety analyses will be based on data from the TE period for the Treatment Period for all subjects in the corresponding Safety Set for the Treatment Period, unless otherwise specified. Subjects will be analyzed according to the treatment group (ELX/TEZ/IVA or control) they actually received in the Treatment Period. For listing purpose, both the treatment group (ELX/TEZ/IVA or control) and the treatment (ELX/TEZ/IVA or TEZ/IVA or IVA) a subject receives will be presented. For subjects receiving study drug from more than one treatment, the treatment allocation will be the higher treatment (ELX/TEZ/IVA > TEZ/IVA > IVA).

The overall safety profile of study drug will be assessed in terms of the following safety and tolerability endpoints:

- Treatment-emergent adverse events (TEAEs)
- Clinical laboratory values
- ECGs
- Vital signs
- Pulse oximetry

Only descriptive analysis of safety will be performed, and no statistical testing will be performed. The safety data during the Run-in Period will only be presented in listings, unless otherwise specified.

9.4.1 Adverse Events

For analysis purposes, AEs will be classified as pretreatment AEs, TEAEs during the Run-in Period, TEAEs during the Treatment Period, and post-treatment AEs, defined as follows:

Pretreatment AE: any AE that occurred before the first dose date of study drug (TEZ/IVA or IVA) in the Run-in Period

TEAE during the Run-in Period: any AE that worsened (either in severity or seriousness) or that was newly developed at or after the first dose date of study drug (TEZ/IVA or IVA) through the end of the TE period for the Run-in Period

TEAE during the Treatment Period: any AE that worsened (either in severity or seriousness) or that was newly developed at or after the first dose date of study drug (TC or placebo+TEZ/IVA or placebo+IVA) through the end of the TE period for the Treatment Period

Post-treatment AE: any AE that worsened (either in severity or seriousness) or that was newly developed after:

- the TE period for Run-in Period if the subject did not receive treatment in the Treatment Period
- the TE period for the Treatment Period if the subject received treatment in the Treatment Period

For AEs with completely missing or partially missing start dates, if there is no clear evidence that the AEs are pre-treatment or TEAE during the Run-in Period or post-treatment, the AEs will be classified as TEAEs corresponding to the Treatment Period. Unless otherwise specified, TEAE refers to TEAE during the Treatment Period.

Details for imputing missing or partial start dates of adverse events are described in [Appendix E](#).

An overview of all TEAEs by treatment group and overall will be summarized in the following categories:

- Number of TEAEs (total number of TEAEs only)
- Subjects with any TEAEs
- Subjects with TEAEs by strongest relationship
- Subjects with TEAEs by maximum severity
- Subjects with TEAEs leading to study drug discontinuation (discontinuation of any study drugs)
- Subjects with TEAEs leading to study drug interruption (interruption of any study drugs)
- Subjects with Grade 3/4 TEAEs
- Subjects with related TEAEs
- Subjects with serious TEAEs
- Subjects with related serious TEAEs
- Subjects with TEAE leading to death

The following summary tables of TEAEs will be presented by treatment group:

- All TEAEs
- Grade 3/4 TEAEs
- TEAEs by strongest relationship

- TEAEs by maximum severity
- TEAEs leading to treatment discontinuation
- TEAEs leading to treatment interruption
- Related TEAEs
- Serious TEAEs
- Related serious TEAEs
- TEAEs leading to death

Summaries will be presented by MedDRA System Organ Class (SOC) and Preferred Term (PT) using frequency counts and percentages (i.e., number and percentage of subjects with an event). When summarizing the number and percentages of subjects, subjects with multiple occurrences of the same adverse event or a continuing adverse event will be counted once, and only the maximum severity level will be presented in the severity summaries, and the strongest relationship level in the relationship summaries.

Additional summary tables will be presented by treatment group for TEAEs showing number and percentage of subjects

- All TEAEs by PT

All AEs, including pretreatment AEs, TEAEs for all applicable periods, and post-treatment AEs, will be presented in an individual subject data listing based on the All Subjects Set. In addition, separate listings containing individual subject adverse event data for TEAEs leading to treatment discontinuation, TEAEs leading to treatment interruption, Grade 3/4 TEAEs, SAEs and all deaths will be provided separately, with a flag indicating the TEAE status for SAEs and deaths.

In addition, the following tables for the Run-in period will be presented by overall based on the Safety Set for the Run-in period.

- An overview of TEAEs during the Run-in Period
- All TEAEs during the Run-in Period by SOC and PT

